we and others have also reported that in this timeframe, approximately 20-25% of CIN2/3 lesions associated with HPV16 will undergo regression [63]. Lesions that are associated with HPV genotypes other than HPV16 are even more likely to regress in this timeframe [64]. Moreover, in this population, it is feasible to visualize directly, quantitate serially, and perform therapeutic resection of premalignant lesions. Based on safety and tolerability data in pediatric populations receiving intrarectal suppositories at a dose that is approximately five-fold compared to the regimen we propose in this clinical protocol, we do not expect dose-limiting toxicities with the dosage and regimen proposed in this proof-of-principle study. The [name] group has a decade of experience in the design and execution of prospective clinical protocols specific for this patient cohort, testing immunotherapeutic interventions prior to standard therapeutic resection of any residual lesions. [65, 66]. The parallel design of this trial will allow comparison of tissue-based endpoints in this cohort.

Despite the experience with active immunotherapy in other tumor models, it is still not clear what measures of immune response are relevant to lesion regression. In particular, it does not appear that classic measures of immune response, measured in the circulation, correlate at all with clinical response. Because the biology of HPV disease is extensively characterized; because there are known, quantifiable risk factors for persistence and progression of disease; because we have ready access to an immunocompetent population of patients at elevated risk for carcinoma development; and because we can directly visualize and subsequently therapeutically resect and analyze affected tissue; we are presented with an opportunity to rapidly evaluate therapeutic regimens, characterize relevant immune responses, and provide direction for future interventions, both in this disease and in other tumor models. The relatively long precursor phase in HPV disease also provides many opportunities for intervention, including, optimally, prophylaxis against the development of cancer.

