### **9.1 Subject Inclusion Criteria**

- \* Patients with high-grade cervical intraepithelial lesions (CIN2/3) confirmed by colposcopy and biopsy.
- \* Patients who have measurable disease after diagnostic biopsy.
- \* Patients who weigh  $\geq 50$  kg
- \* Patients who are HPV-positive by DNA test
- \* Patients who are age 18 or older.
- \* Patients who are able to give informed consent.
- \* Patients who are immunocompetent.
- \* Patients who are not pregnant; committed to using adequate contraception through week 15 if of childbearing age. Condom use will be encouraged.
- \* Patients who have the ability to collaborate planned follow-up

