At the end of dose escalation phase, one dose will be selected for the expansion phase from dose levels II-IV that are considered safe. In general, the lowest dose level with significant within subject decreases in viral load (from baseline at Week 15) and lesion clearance to CIN1 or less will be selected (see Section 12.2 for details). If none of the safe doses achieve significance for decrease in viral load and lesion clearance, a decision will be made based on the totality of safety and efficacy profiles of the dose levels considered safe.

A cohort of 12 patients will be enrolled and treated at the selected dose level at the expansion phase to further evaluate the safety and efficacy of Artesunate.

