## **12.2 Secondary Endpoints**

Secondary endpoints include change in histology (CIN2/3 or no CIN2/3) at week 15 and changes in cervical HPV viral load. These endpoints are chosen because in other trials they have been shown to be quantifiable and reproducible. They do reflect the biology of HPV infection and cervical intraepithelial disease, and furthermore have been shown to be modulated in response to intervention in other trials.[67] The histological outcome will be determined by comparing the initial diagnostic biopsy used for protocol entry with the exit cone resection. HPV viral load will be ascertained from longitudinally obtained cervical cell samples, using quantitative PCR.[68] This data will be used to estimate the regression rate within the fifteen-week window in the exploratory analysis.

Secondary endpoints will also include change in lesion size by colposcopy, and characterization of peripheral and local tissue response to the suppository. These measures will be correlated with clinical response, and with preclinical experimental data in the exploratory analysis. In every case possible, changes in lesion size by colposcopy will be ascertained by analyzing serially obtained digital colposcopic images. Measures of immune response will be ascertained on serially obtained peripheral blood specimens, and on flash frozen tissue from the therapeutic resection specimens.

To test that HPV viral load is different during and after treatment as compared to before treatment, paired t-tests and signed rank tests will be used. Log transformation (or other appropriate transform) will be performed to symmetrize the distributions and achieve normality. For each of these variables, a paired t-test will be performed. Due to the small sample size and potential non-normality of the data, the non-parametric signed rank test will also be used. The paired t-test tests whether or not the mean HPV viral loads at baseline and follow-up are

equivalent, whereas the Wilcoxon matched-pairs signed-ranks test tests whether the distributions of HPV viral loads is the same at baseline and follow-up.

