### 12.4 Additional exploratory analysis

In addition to hypothesis testing, we will characterize the change in HPV viral load over the course of the trial using longitudinal data modeling. For each individual, we will have data on HPV viral load at weeks -2 (Screening visit), 9-10, and 15. A random effects model will be used to model the distribution of HPV viral load over time:

$$hpv_{it} = \beta_{0i} + \beta_1 t + \beta_2 t^2 + \varepsilon_{it}$$

where  $hpv_{it}$  is individual  $i$ 's HPV viral load at week  $t$ . Correlations between observations within an individual are accounted for by the random intercept (i.e. random effect) term. A quadratic model is used to account for non-linearity in the change of HPV viral load. From the fitted model, we can estimate the effect of the vaccine treatment on viral load. The plot below is based on simulated data and shows the type of result we hypothesize: a downward trend in HPV viral load that flattens as time increases. Based on the random effects model shown above, we can estimate the average response (denoted by the thick line) and better understand the association between the vaccine and response and specifically when changes in viral load tend to occur.

Lesion size will also be described using the random effects linear longitudinal model described above to look for time trends.

The secondary efficacy endpoints will be compared with analogous data obtained in a currently open cohort study, “Evaluation of Tissue and Peripheral Blood Immune Response in Women with HPV16+ Cervical Intraepithelial Lesions” (Johns Hopkins IRB# NA\_00037578). This observational cohort protocol has been open since 1999, and currently includes over 250 subjects. These subjects have the same eligibility criteria as the criteria for this trial, and are followed prospectively for the same timeframe, before undergoing standard therapeutic resection at week 15. To date, no CIN2/3 lesions have progressed to invasive disease in this timeframe, which is well within the standard of care. We will compare changes in HPV viral load and lesion size from baseline at Week 15, rates of histologic regression, and change in viral load over the 15 week window, in both cohorts.

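### The expansion-level rule tests viral load against no change and names no test for lesion clearance, so spontaneous regression can produce a false activity signal and favour fewer cycles

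*Combined protocol and SAP*

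**What the plan says.** Section 12.1 chooses one of the safe levels II-IV for a 12-patient expansion. The general rule is to take "the lowest dose level with significant within subject decreases in viral load (from baseline at Week 15) and lesion clearance to CIN1 or less", with Section 12.2 cited for the details. A fallback applies "If none of the safe doses achieve significance for decrease in viral load and lesion clearance": the choice is then made on the overall safety and efficacy picture of the safe levels.

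Section 12.2 gives two tests for viral load, a paired t-test and a signed-rank test, both against baseline: "The paired t-test tests whether or not the mean HPV viral loads at baseline and follow-up are" the same. For histology it says "The histological outcome will be determined by comparing the initial diagnostic biopsy used for protocol entry with the exit cone resection", and it names no significance test.

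Section 5.0 describes what happens without the drug. Over this timeframe "approximately 20-25% of CIN2/3 lesions associated with HPV16 will undergo regression", and "Lesions that are associated with HPV genotypes other than HPV16 are even more likely to regress in this timeframe". Section 9.1 admits any HPV-positive woman, not only those with HPV16.

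External comparisons are planned elsewhere. Section 7.2 names a chi-square test at p < 0.1 against the institution's colposcopy database, covering lesion clearance and CIN regression. Section 12.4 adds an observational cohort of over 250 women: "We will compare changes in HPV viral load and lesion size from baseline at Week 15, rates of histologic regression". Neither section is mentioned in the selection rule.

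**The concern.** Section 5.0 says the aim is to expand the cohort with the fewest cycles that shows a therapeutic effect. A test against the woman's own baseline does not show that when some lesions regress untreated. If a lesion that regresses also loses viral load, the mean change in an inert cohort is below zero, and the paired tests reject more often than their nominal level.

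For clearance the plan leaves open what counts as significant. The choice of test largely determines how well this half of the rule protects against natural regression.

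The direction of the error matters because the lowest qualifying level is taken. A chance pass at level II (one cycle of 200 mg) comes ahead of levels III and IV, even if only the multi-cycle regimens work. The expansion cohort would then start with an activity signal that natural history could explain.

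**Working it through.** **Inputs from the documents.** Each candidate level has 9 women, or 12 after one DLT, and dropouts are replaced (Section 12.1). As a check on this reading, 3 + 3 × (9 + 3) = 39, which matches the stated maximum for escalation. The plan gives no operating characteristics for the selection rule, so there is no figure of its own to reproduce. Untreated regression is 0.20-0.25 for HPV16 (Section 5.0) and higher, without a figure, for other types. No alpha is stated for the rule. I use 0.10 two-sided, because 0.10 is the exploratory threshold in the synopsis.

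**Assumptions not in the documents.** Women who regress lose 1-3 log10 of viral load and the others have mean change zero. The SD of change is 0.5-1.0 log10. For non-HPV16 types I use 35% regression as an illustration.

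**Step 1: clearances in an inert cohort of 9.** P(X ≥ r), with X ~ Binomial(9, p):

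| r | p = 0.20 | p = 0.25 | p = 0.35 (assumed) |
|---|---|---|---|
| 1 | 0.87 | 0.92 | 0.98 |
| 3 | 0.26 | 0.40 | 0.66 |
| 4 | 0.086 | 0.166 | 0.39 |
| 5 | 0.020 | 0.049 | 0.17 |

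**Step 2: what significant clearance could mean on a within-subject test.** All women enter with CIN2/3 ("Patients with high-grade cervical intraepithelial lesions (CIN2/3) confirmed by colposcopy and biopsy"), so change can only be in one direction.
- Exact two-sided McNemar, p = 2 × 0.5^r: 3/9 gives 0.25, 4/9 gives 0.125 and 5/9 gives 0.0625. At 0.10 it needs 5/9.
- Uncorrected McNemar chi-square, r²/r = r on 1 df: 2/9 gives p = 0.157 and 3/9 gives p = 0.083. At 0.10 it needs 3/9.

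**Step 3: viral load in an inert cohort of 9.** Simulated paired t-test, counting only significant decreases at two-sided 0.10 (nominal 5% in that direction):
- 20% regression: 12% (fall 1, SD 1.0) to 24% (fall 3, SD 0.5).
- 25% regression: 15% (fall 1, SD 1.0) to 34% (fall 3, SD 0.5).

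The signed-rank test gives about 12-28% over the same settings. If non-regressors also drift down by 0.25-0.5 log10, the t-test figure rises to 38-70% (falls of 2-3 log10, SD 1.0).

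**Step 4: both limbs together, no drift, 20-25% regression, per inert cohort.**
- Significant viral-load fall and at least 5/9 cleared: about 1-5%.
- Significant viral-load fall and at least 3/9 cleared: about 6-29%.

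The first range cannot exceed the Step 1 tail for 5/9 (0.020-0.049), whatever is assumed about viral load. The second depends on the assumed falls and SDs.

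**The case against.** A reader might infer that clearance is also tested against no change, that is against 0%. The phrase about within-subject decreases and the entry-versus-exit comparison in Section 12.2 point that way, but no such test is stated. The only test the plan names for clearance is the external chi-square in Section 7.2, and one fair reading is that significant clearance already means that test. What the documents support is that the rule does not say which test applies.

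A reader might also let any clearance count, since at least one of nine inert-treated women clears with probability 0.87-0.92. That does not model the rule, which asks for significance: 1/9 gives p = 1.0 by exact McNemar and 0.32 without correction. If an exact test needing 5/9 is intended, the clearance limb already holds joint false passes to about 5% or less.

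Nor do the documents support saying that the defect causes an inert level to be expanded. The rule is worded as a general one, and the fallback expands a safe level with or without significance. If every level is inert, an inert level is expanded either way. Safety is the primary outcome and the analysis is described as mainly descriptive.

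These points narrow the concern. They do not remove it: viral load is tested against no change, no clearance test is tied to the rule, and the natural-history comparisons are not linked to selection.

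**Conclusion.** The concern holds in limited form. The viral-load limb has the wrong null for finding a drug effect. It signals a fall in roughly 12-34% of inert cohorts instead of 5%, given the assumed falls and SDs. The joint false-pass rate is about 1-5% per cohort or about 6-29%, depending on a clearance test the plan does not name. The binomial figures for HPV16 rest only on the protocol's regression rate and n = 9; the viral-load figures and the 6-29% range rest on assumptions.

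The harm is a false activity signal and a tilt towards fewer cycles at the same 200 mg dose. This should be fixed before cohort results are seen, but it does not undermine the primary safety objective.

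**What to change.** Tie the selection rule in Section 12.1 to the comparisons already planned in Sections 7.2 and 12.4.

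1. **Viral load.** Compare each cohort's week-15 log10 change with the observational cohort's 15-week change by one named rank test, with alpha and sidedness stated.
2. **Clearance.** Use a one-sided exact binomial test against a prespecified natural-history regression rate, with alpha stated. With 9 women, a 25% benchmark needs 5/9 (p = 0.049; 4/9 gives 0.166), and a 20% benchmark needs 4/9 (p = 0.086). For a level extended to 12 women, the thresholds at alpha 0.10 are 6/12 (p = 0.054) and 5/12 (p = 0.073).
3. **Genotype.** The observational cohort is HPV16+ by its title, although Section 12.4 says its eligibility criteria match this trial's. Confirm which applies. If it is HPV16 only, use it directly for HPV16-positive women and prespecify a justified higher benchmark for the rest, for example from the colposcopy database. A single 25% benchmark would not be enough: at an assumed 35% regression, 5/9 occurs by chance 17% of the time.
4. Keep the existing fallback.

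**Cost.** The change is to the SAP wording, plus the work of justifying the non-HPV16 benchmark. The 5/9 rule has power of only 0.50 if true clearance is 50% and 0.73 if it is 60%, so the fallback judgement will be used more often.

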## **12.2 Secondary Endpoints**

Secondary endpoints include change in histology (CIN2/3 or no CIN2/3) at week 15 and changes in cervical HPV viral load. These endpoints are chosen because in other trials they have been shown to be quantifiable and reproducible. They do reflect the biology of HPV infection and cervical intraepithelial disease, and furthermore have been shown to be modulated in response to intervention in other trials.[67] The histological outcome will be determined by comparing the initial diagnostic biopsy used for protocol entry with the exit cone resection. HPV viral load will be ascertained from longitudinally obtained cervical cell samples, using quantitative PCR.[68] This data will be used to estimate the regression rate within the fifteen-week window in the exploratory analysis.

Secondary endpoints will also include change in lesion size by colposcopy, and characterization of peripheral and local tissue response to the suppository. These measures will be correlated with clinical response, and with preclinical experimental data in the exploratory analysis. In every case possible, changes in lesion size by colposcopy will be ascertained by analyzing serially obtained digital colposcopic images. Measures of immune response will be ascertained on serially obtained peripheral blood specimens, and on flash frozen tissue from the therapeutic resection specimens.

To test that HPV viral load is different during and after treatment as compared to before treatment, paired t-tests and signed rank tests will be used. Log transformation (or other appropriate transform) will be performed to symmetrize the distributions and achieve normality. For each of these variables, a paired t-test will be performed. Due to the small sample size and potential non-normality of the data, the non-parametric signed rank test will also be used. The paired t-test tests whether or not the mean HPV viral loads at baseline and follow-up are

equivalent, whereas the Wilcoxon matched-pairs signed-ranks test tests whether the distributions of HPV viral loads is the same at baseline and follow-up.

### 12.3 Other Efficacy Endpoints

[figure not shown]
In every case possible, change in lesion size from week 0 to week 15 will be measured using serial digital colpographs. Changes in HPV16 E7-specific T-cell response (CD8) will be compared at week 0 to week 15. Differences will be calculated between baseline and follow-up and the appropriate transform performed. Point estimates, confidence intervals, and hypothesis testing (i.e. paired t-test and signed rank test) will be done.

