### **Colposcopic examination**

Patients will undergo serial colposcopic examinations; at the screening visit, and at weeks 6, 15, 28. Exfoliated cell samples will be obtained using Digene swabs at the time of colposcopy, for HPV typing. Specimens for HPV genotyping will be processed by Quest Diagnostics, Nichols Institute. Specimens for quantitation of HPV viral load should be directed to the GYN biorepository, where they will be processed and cryopreserved for batch analysis. Swabs of cervical secretions will be banked in the tissue bank. Cervical lymphocyte samples will be processed directly.

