We will correlate immune response with clinical response by looking at the association with disease regression. A logistic regression analysis will be performed with regression as the outcome and baseline and change between baseline and follow-up HPV viral load as predictors, where HPV viral load and the change have been transformed for normality. Using these two predictors, we can assess how change in viral load is associated with clinical response, adjusting for baseline level. Other predictors of interest will also be evaluated, including measures of E7-specific immune response. To explore the association between continuous outcomes of interest and time, the random effects model described above will be used.

The frequency and severity of all toxicities will be tabulated from CRFs and summarized for review in a descriptive fashion. The initial review of toxicity will be completed after the first treatment group has completed the intervention portion of the study (through week 5).

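### HPV16 E7 response is analysed without regard to HPV genotype although any type is eligible; this dilutes the Section 12.3 change and may bias the exploratory Section 12.4 association in the inverse direction

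*Combined protocol and SAP*

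**What the plan says.** Eligibility (Section 9.1, and likewise the Synopsis) asks for "Patients who are HPV-positive by DNA test" and names no genotype.

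Section 12.3 makes the immune measure type-specific: "Changes in HPV16 E7-specific T-cell response (CD8) will be compared at week 0 to week 15". It adds that "hypothesis testing (i.e. paired t-test and signed rank test) will be done", and names no subset of women.

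Section 12.4 turns to the clinical link: "We will correlate immune response with clinical response by looking at the association with disease regression". The logistic model has lesion regression as outcome and baseline and change in viral load as predictors. Then: "Other predictors of interest will also be evaluated, including measures of E7-specific immune response". Genotype is not named as a covariate or stratum.

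Section 5.0 gives the background rates. It says that, in this timeframe, "approximately 20-25% of CIN2/3 lesions associated with HPV16 will undergo regression", and then: "Lesions that are associated with HPV genotypes other than HPV16 are even more likely to regress in this timeframe". It gives no figure for the other types.

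Genotype is available. Table 3 schedules genotyping at screening and at later visits, and Section 10.4 says "Specimens for HPV genotyping will be processed by Quest Diagnostics, Nichols Institute". No part of the plan uses the result in the immune analyses.

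**The concern.** An HPV16 E7 assay measures a response to one viral type. In a woman whose lesion carries another type, such a response may well be absent or have nothing to do with that lesion. The plan names no rule for including or separating these women.

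Two different consequences follow. In the paired comparison of Section 12.3, women with little or no change pull the mean towards zero; this is dilution only. In the logistic analysis of Section 12.4, genotype may be related to both sides of the model. By the protocol's own account non-HPV16 lesions regress more often, and the women who carry them may seldom show an HPV16 E7 response. Pooling would then make response look tied to less regression, and could hide or reverse a true positive correlate.

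The Synopsis lists correlating immune response with clinical response among the secondary and exploratory objectives. It also says exploratory results at p of 0.10 or less will be considered for study in later trials. A misleading correlate could therefore be carried forward.

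**Working it through.** The plan states no power or error rate for these analyses, so there is no figure to reproduce.

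**Inputs from the protocol.** HPV16 regression *a* = 20-25%, midpoint 22.5% (Section 5.0). Non-HPV16 regression *q* is higher, with no figure (Section 5.0). Sample size is 30 (Synopsis), or 30 + 12 = 42 if the expansion cohort of Section 12.1 is additional. The exploratory threshold is p ≤ 0.10 (Synopsis).

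**Assumed, not in the protocol.** HPV16 share *p* = 40-60%; *q* = 30-50%; E7 responder share *s* = 40% in HPV16 women and *f* = 0 or 10% in the others.

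**1. Dilution in Section 12.3.** Pooled mean change = *p*·Δ(HPV16) + (1 − *p*)·Δ(other). With Δ(other) = 0 this is *p*·Δ(HPV16), so the estimate falls to 40-60% of its value in HPV16 women. The test itself loses less. With a true change of 1 SD in HPV16 women, no mean change and a spread of 0.2 SD in the others, and N = 30, simulated paired t-test power at the 5% level (pooled against HPV16 only) was 81% against 85-86% at a 40% share, 91-92% against 93% at 50%, and 96-97% against 97% at 60%.

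**2. Pooled odds ratio in Section 12.4, with no link inside either genotype group.**

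- Regression in responders = [*p s a* + (1 − *p*) *f q*] / [*p s* + (1 − *p*) *f*]
- Regression in non-responders = [*p*(1 − *s*) *a* + (1 − *p*)(1 − *f*) *q*] / [*p*(1 − *s*) + (1 − *p*)(1 − *f*)]

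Take *p* = 0.5, *a* = 0.20, *q* = 0.40, *s* = 0.4.

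- *f* = 0: responders 20%; non-responders (0.06 + 0.20)/0.80 = 32.5%. Odds ratio = (0.20/0.80)/(0.325/0.675) = 0.52.
- *f* = 0.10: responders (0.04 + 0.02)/0.25 = 24%; non-responders (0.06 + 0.18)/0.75 = 32%. Odds ratio = (0.24/0.76)/(0.32/0.68) = 0.67.

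Over the whole grid the odds ratio is 0.35-0.87 for *f* = 0 and 0.57-0.91 for *f* = 10%. If *f* = *s*, it is 1 and the bias is gone.

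**3. A true link, pooled** (*a* = 22.5%, *f* = 0). A true odds ratio of 2 inside HPV16 women means 29.9% regression in responders and 17.6% in non-responders. At *p* = 0.5 and *q* = 0.40, pooled non-responders regress at (0.3 × 0.176 + 0.5 × 0.40)/0.8 = 31.6%, and the odds ratio becomes (0.299/0.701)/(0.316/0.684) = 0.92. Over the grid, a true 2 appears as 0.62-1.34 and a true 3 as 0.78-1.76.

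**4. False-positive rate.** Simulation of 6,000 runs per setting: score test of regression on a continuous E7 change, E7 as the only predictor, two-sided 10% level, *a* = 22.5%, E7 change distributed as in step 1. Ranges are over HPV16 shares of 40%, 50% and 60%.

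| Non-HPV16 regression | N = 30 | N = 42 |
|---|---|---|
| 22.5% (no difference) | 10.2-10.4% | 10.0-10.6% |
| 30% | 9.6-11.1% | 10.6-11.5% |
| 40% | 13.7-15.1% | 16.9-17.6% |
| 50% | 21.2-23.0% | 26.7-29.3% |

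The excess is almost all in the inverse direction: at N = 30, a 40% share and 50% non-HPV16 regression, 22.5 of the 23.0 percentage points.

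**5. HPV16-positive women only.** The odds ratio is 1 when there is no link. The simulated rejection rate is 10.5-12.0%, whatever the non-HPV16 regression rate. The set is 30 × 0.4 = 12 to 30 × 0.6 = 18 women, with 12 × 0.225 = 2.7 to 18 × 0.225 = 4.1 regressions expected.

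**The case against.** The defence has several sound points.

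- **The 12.3 test cannot create a link to regression.** Genotype is taken as fixed within a woman, and regression is not in that comparison. A reader might infer that the paired test is confounded; it is only diluted. The confounding can arise only in Section 12.4.
- **The wording of 12.4 is looser.** It says E7-specific, without HPV16, and Section 10.4 speaks of responses to HPV antigens in general. Reading 12.4 as HPV16 E7 is natural after 12.3, but it is an inference.
- **The key conditions are not stated.** A reader might infer that all women are certainly pooled, or that non-HPV16 women certainly count as non-responders. The plan is silent on the subset and gives no response rate by genotype. Its list of further predictors is open, so genotype is not excluded.
- **The size is uncertain.** At 30% non-HPV16 regression the false-positive inflation with 30 women is negligible. Noise is also larger than the bias. Take 30 women, half HPV16-positive, half of those responding, and regression of 22.5% against 40%. Responders then number 7.5 with 1.7 regressions, the odds ratio is 0.56, and its log has a standard error of about 0.98, so the 95% interval is roughly 0.08 to 3.8. The bias is about 0.6 of a standard error.
- **The stakes are limited.** The Synopsis calls the analysis primarily descriptive, and Section 5.0 already doubts that circulating immune measures correlate with clinical response.

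These points limit the claim without removing it. An HPV16-specific readout in a mixed-genotype population, with a named prognostic difference by genotype and the genotype in hand, needs a stated rule.

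**Conclusion.** The concern holds in a limited form. As written, the E7 analyses in Sections 12.3 and 12.4 take no account of genotype in a population open to any HPV type. If non-HPV16 women rarely show an HPV16 E7 response, the 12.3 mean change falls to the HPV16 share of its value (40-60% under the assumed share), and the 12.4 association may be pulled below 1, to about 0.35-0.9 with no true link. False-positive inflation at 30 women runs from negligible to about double the nominal 10%.

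This rests on the assumed HPV16 share, non-HPV16 regression rate and response rates. Only the HPV16 regression rate and the direction of the genotype difference come from the protocol. The odds ratios and error rates are for E7 as sole predictor, not for the model with viral-load terms.

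A reader might infer that the trial's main conclusions are at risk. They are not: safety is the primary outcome, and expansion-dose selection in Section 12.1 names viral load and lesion clearance, not E7 response. Nor does this point show that every other immune or viral-load analysis must be split by genotype.

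**What to change.** **Section 12.3.** Make the paired HPV16 E7 analysis in women HPV16-positive on the screening genotype the main one. Report the E7 results of other women descriptively.

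**Section 12.4.** Name the antigen. Examine the association of E7 response with regression within HPV16-positive women, or stratified by or adjusted for HPV16 versus other. Keep it to a descriptive table or a single E7 predictor: about 3-4 expected regressions cannot support a logistic model with two viral-load terms and an E7 term.

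**Cost.** Wording only; Table 3 already schedules the genotype, so no visit, sample or assay is added. The price is a smaller E7 set, about 12-18 of 30 women at a 40-60% HPV16 share, and a correspondingly imprecise association. The stratified or adjusted form keeps all women in the analysis, but those from a group with almost no responders would add little to the E7 estimate.
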